8 ASSESSMENT OF SAFETY

Side effects of CVR use: As noted above, the NuvaRing has an acceptable safety profile, is approved for use by the U.S. F.D.A., and is widely used by U.S. women for contraception. We will routinely query participants prior to use for any contraindications to CVR use, and also carefully assess at each visit for the development of any interim clinical processes of concern (for example, thrombosis) that might represent a side effect of the CVR as listed in the package insert. Participants will also be asked to contact us at any time during the study should they have concerns about new symptoms or signs.

Management of adverse events & counseling related to CVR: Participants will receive standard counseling about anticipated side effects of CVR initiation, and will be assessed for any adverse events reported during the course of the study as needed. The main adverse event we anticipate is irregular bleeding among women who use the CVR continuously; this is typically mild and resolves within first two cycles of use. [name], a collaborator on this project, is highly trained in management of contraceptive use, and will provide expert guidance as needed.

Phlebotomy: May cause some pain or bruising. Some persons may feel light-headed or faint when blood is drawn.

Collection of swabs and cervicovaginal samples from genital areas: If samples are collected during herpes episodes, this may cause some irritation from the already sore lesion. Collection of swabs does not pose risk of additional infection.

IUD risk: There is a very small risk that the IUD could be pulled out at the time of pelvic exam or during sample collection.

Data collection: Participants may feel some stress or discomfort answering personal and sensitive questions about their health and sexual practices.

Pelvic/genital examination: Discomfort should be similar to that experienced for a PAP test. There may be a feeling of pressure from the speculum, which may be used to hold the vaginal walls open.

Participants may briefly feel pressure when the swab touches the cervix when samples are taken for bacterial or viral cultures.

Side effects of oral and intravaginal metronidazole gel: These medications may be needed to treat BV during study participation. Interactions between oral metronidazole and alcohol can produce nausea, vomiting, and flushing. Alcohol should be avoided while taking oral metronidazole or using intravaginal metronidazole gel. Yeast infections may be associated with metronidazole gel. Participants will be checked for a yeast infection if they develop symptoms during the study.

Risks of vaginal biopsy: Patients may experience pain associated with the speculum examination. They also may have pain associated with lidocaine injection and the biopsy. There are small risks of bleeding and infection. Risk of bleeding will be minimized by biopsy location along the upper anterior or posterior aspect of the vagina, use of lidocaine with epinephrine, observation and use of silver nitrate or Monsel's solution to ensure hemostasis. To minimize the risk of delayed bleeding, participants will be instructed to avoid sexual intercourse or placement of tampons for 5 days. Subjects will be instructed to not begin collecting vaginal swabs until 5 days after the biopsy to ensure healing. All procedures will be performed by a board-certified gynecologist or experienced nurse practitioner who has performed vaginal biopsies for other research studies.

8.1 Known Potential Benefits

Subjects may benefit from participation in this study by having a blood test for detection of infection with HSV2 and HIV, and by finding out more about the likelihood of their having BV or recurrent BV. They will not be charged for any of the diagnostic tests. Subjects may benefit from pre and post-test counseling, treatment and referrals, as necessary. We have found that subjects are empowered by knowing how frequently they shed HSV-2, for example, and by knowing more about what BV is and how it can be prevented. Otherwise, this study will not be of direct benefit to the subjects.

8.2 Specification of Safety Parameters

Safety will be assessed by the frequency, incidence and severity of AEs and SAEs solicited in-clinic and via phone call.

8.3 Methods and Timing for Assessing, Recording, and Analyzing Safety Parameters

8.4 Adverse Events, Serious Adverse Events

The investigator is responsible for ensuring all AEs that are observed or reported during the study are documented.

8.4.1 Definition of Adverse Event

Adverse Event: International Conference on Harmonisation (ICH) guideline E6 defines an AE as any untoward medical occurrence in a patient or clinical investigation subject administered a pharmaceutical product regardless of its causal relationship to the study treatment. An AE can therefore be any unfavorable and unintended sign (including an abnormal laboratory finding), symptom, or disease

temporally associated with the use of medicinal (investigational) product. The occurrence of an AE may come to the attention of study personnel during study visits and interviews or by a vaccine recipient presenting for medical care.

Severity of Event: All AEs will be assessed by the clinician using a standard grading system (NIH DAIDS Adverse Events Toxicity Tables). For events not included in the protocol defined grading system, the following guidelines will be used to quantify intensity:

Mild: events require minimal or no treatment and do not interfere with the patient's daily activities.

Moderate: events result in a low level of inconvenience or concern with the therapeutic measures. Moderate events may cause some interference with functioning.

Severe: events interrupt a patient's usual daily activity and may require systemic drug therapy or other treatment. Severe events are usually incapacitating.

Life threatening: any adverse drug experience that places the patient or subject, in the view of the investigator, at immediate risk of death from the reaction as it occurred, i.e., it does not include a reaction that had it occurred in a more severe form, might have caused death.

Relationship to study procedures: The investigator's assessment of the relationship of an AE to study procedures is part of the documentation process. If there is any doubt as to whether a clinical observation is an AE, the event should be reported to the PI. AEs will be assessed according to the relationship to the study process: associated or not associated. To help assess, the following guidelines are used.

Associated – The event is temporally related to the study procedures and no other etiology explains the event.

Not Associated – The event is temporally independent of study the study procedures and/or the event appears to be explained by another etiology.

8.4.2 Definition of Serious Adverse Event

A SAE is defined as an AE meeting one of the following conditions:

- Results in death during the period of protocol defined surveillance.
- Is life-threatening (defined as a subject at immediate risk of death at the time of the event).
- Requires inpatient hospitalization or prolongation of existing hospitalization during the period of protocol-defined surveillance.
- Results in congenital anomaly or birth defect.
- Results in a persistent or significant disability/incapacity.
- Any other important medical event that may not result in death, be life threatening, or require hospitalization, may be considered an SAE when, based upon appropriate medical judgment, the event may jeopardize the subject and may require medical or surgical intervention to prevent one of the outcomes listed above. Examples of such medical events include allergic bronchospasm requiring intensive treatment in an emergency room or at home, blood

dyscrasias or convulsions that do not result in inpatient hospitalization, or the development of drug dependency or drug abuse.

8.5 Reporting Procedures

Adverse events including local and systemic reactions not meeting the criteria for SAEs will be captured on the appropriate CRF. Information to be collected includes event description, date of onset, investigator assessment of severity, investigator assessment of relationship to study product, date of resolution of the event, seriousness, and outcome. The **intensity** of nonserious AEs can be assessed by a licensed clinician (i.e., physician, nurse, Nurse Practitioner, Physician Assistant). **Causality** of nonserious AEs can be assessed only by a clinician licensed to make medical diagnoses (ie, physician, Nurse Practitioner, Physician Assistant). All AEs occurring while on study will be documented appropriately regardless of relationship. All AEs will be followed to adequate resolution or until considered stable.

Any medical condition that is present at screening will be considered as baseline and will not be reported as an AE. If the severity of any pre-existing medical condition increases during the study period, then it will be recorded as an AE.

All SAEs will be reported immediately to the Investigator.

SAE Contact: [name] PI.

[contact], [contact], [contact], cell [contact]

SAE Alternate: A physician from the Virology Research Clinic is available at any time by calling the clinic pager at [contact].

The SAE report will include the following information (as available)

- Patient ID
- Description of SAE (onset date, severity, causal relationship)
- Basic demographic information
- Outcomes attributed to the event
- Summary of relevant test results, laboratory data, and other relevant history
- The first and last dates of study drug administration
- Statement whether study drug was discontinued or schedule modified
- Statement whether the event abated after study drug was discontinued or schedule modified
- Statement whether the event recurred after reintroduction of the study drug if it had been discontinued.

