infections, and acquisition of multiple STI, including HSV2 and HIV.¹⁴ BV may elevate these risks in several ways, including activation of local immune cells. Finally, recent data indicate that onset of menstruation triggers key shifts in local vaginal bacteria, and in many women, may actually precipitate BV. Continuous use of the NuvaRing (use for four weeks, then replace) suppresses menstruation, and is increasingly used by many women with excellent reports of acceptability and safety. Whether this suppression of menstruation could suppress BV recurrence is not known.

Although short-term antibiotic therapy improves symptoms and restores *Lactobacillus* predominance in most women with BV, up to 20% of women fail routine therapy. In addition, BV recurrence after successful therapy is the rule. Recurrence is likely caused by failure to recolonize the vagina with desirable lactobacilli, which requires adequate vaginal estrogenization. In one study, women who used the NuvaRing for 3 consecutive 28-day cycles had higher quantities of desirable vaginal lactobacilli relative to women who used oral contraceptive pills containing 20 µg ethinyl estradiol and 100 µg levonorgestrel.¹ The NuvaRing releases 120 mcg/day of ENG (the active metabolite of desogestrel, a progesterone) and 15 mcg/day of ethinyl estradiol (the estrogen component). While generally well tolerated, incidence of local complaints (increased vaginal discharge or discomfort) with continuous CVR use is higher than those reported by OC users;¹⁵ thus, the risk: benefit ratio of this approach needs careful assessment.

Pregnancy is also an independent risk for HIV acquisition and transmission, when acquisition confers high rates of perinatal transmission.^{16,17} However, systemic depot progesterone, commonly used worldwide, may independently increase risk of HIV acquisition and transmission.⁸ Increased HIV risk related to hormonal contraceptive use would be of global public health importance, given the large number of women using such methods. In a recent technical report, the World Health Organization noted that “expansion of contraceptive method mix and further research on the relationship between hormonal contraception and HIV infection is essential.”¹⁸

For all of these reasons, then, a careful study of the microbiological, clinical, and immunologic benefits of the CVR is a high scientific and public health priority.

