4 STUDY ENROLLMENT

4.1 Eligibility Criteria

- Women who are 18 years of age or older
- BV+ by Amsel criteria and Nugent score OR history of BV in the prior 12 months
- Premenopausal (as defined by having had at least 3 menstrual periods in the last 6 months, unless using hormonal contraception in which the investigators will use clinical discretion in determining eligibility).
- Willing to stop hormonal contraception
- Willing to use the NuvaRing as directed
- Not intending or wishing to become pregnant over the course of the study
- Daily access to a freezer for specimen storage
- Capable of providing written informed consent

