9 STATISTICAL CONSIDERATIONS

9.1 Outcomes

Aim 1. The primary outcome will be quantity of *L. crispatus* measured by qPCR at all available follow-up visits and will be compared during five months of CVR use to one month prior to CVR use. Secondary outcomes will be BV defined clinically by Amsel and confirmed by Nugent criteria at any follow-up visit, quantities of other BVAB defined by qPCR assay, and reported genital adverse events. Quantity and presence of other lactobacilli and BVAB species detected by PCR will be assessed using the methods outlined above. All available follow-up observations will be used. Quantity of *L. crispatus* will be log transformed and analyzed using a linear mixed model with subject random effect to account for correlation within person. Binary outcomes will be analyzed using generalized estimating equations with log link and robust standard errors to estimate relative risks while accounting for correlation.

Aim 2. The outcomes of interest will be compared within participants, using each woman as her own control; observations from the time prior to CVR initiation will be compared to those collected during CVR use. We will use methods for Normal data and then use non-parametric approaches or dichotomize and use binomial link GEE if data are highly skewed and cannot be transformed into a Normal distribution. Some analyses will be exploratory; we will compare quantities of several immune mediators noted above by CVR use. These comparisons will not likely be independent, so we will adjust for multiple comparisons by permutation procedure. We will also correlate concentrations of immune mediators with qPCR results in Aim 1 to test the hypothesis that higher concentrations of protective lactobacilli will be associated with higher levels of protective mediators, and lower levels of inflammatory cytokines/chemokines. Continuous variables between comparison groups will be compared using t-tests or Wilcoxon rank-sum tests, and dichotomous variables will be compared by chi-square tests or Fisher's exact tests. Linear mixed effects models or generalized estimating equation (GEE) models will be used to examine whether outcomes (mediator concentrations, vaginal bacterial

quantities) differ significantly between comparison groups after adjustment for confounding factors identified through univariate analysis. All analyses will assume a two-sided significance level of 0.05.

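### The AE baseline is set at screening, about two months before the ring, so a complaint that resolves and returns on the ring at no higher grade may go uncounted

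*Combined protocol and SAP*

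**What the plan says.** The rule is in Section 8.5: "Any medical condition that is present at screening will be considered as baseline and will not be reported as an AE". The next sentence gives the only stated exception: "If the severity of any pre-existing medical condition increases during the study period, then it will be recorded as an AE". Two other sentences bear on capture. Section 8.5 says "All AEs occurring while on study will be documented appropriately regardless of relationship", and Section 8.4.1 says "If there is any doubt as to whether a clinical observation is an AE, the event should be reported to the PI".

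The ring is started at the Month 2 visit (Section 6.3.3; Table 2 footnotes). Women who are BV-positive at screening are treated then and return 7-10 days later to enroll (Sections 6.1 and 6.2). Women who are BV-negative may enroll on the screening day (Section 3). One main-study eligibility criterion is "Willing to stop hormonal contraception", and Section 5.3 starts the hormone-free month after the enrollment visit.

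The protocol names the local effects it expects. Section 1.1 says "incidence of local complaints (increased vaginal discharge or discomfort) with continuous CVR use is higher than those reported by OC users". Section 8 says "The main adverse event we anticipate is irregular bleeding among women who use the CVR continuously". AE rates with ring use are among the secondary objectives in Section 2, and the Aim 1 secondary outcomes in Section 9.1 include "quantities of other BVAB defined by qPCR assay, and reported genital adverse events".

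**The concern.** A baseline for treatment-emergent events should describe the woman just before she is exposed. Here it describes her about two months earlier, in a state that the study then sets out to change. Abnormal discharge is one of the four diagnostic criteria for BV in Section 5.2.1, and women are recruited for BV or a recent history of it. The complaint most likely to be present at screening is therefore also one that the protocol expects from the ring.

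Consider a woman with discharge at screening who is treated, has no symptoms at Month 2, and then has discharge of the same grade on the ring. On the literal wording she has a screening condition that has not worsened, so no AE form is completed. Section 1.1 itself asks for careful assessment of risk against benefit, and the AE rate is the main input to the risk side.

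**Working it through.** The documents give no AE rate to reproduce, so the check consists of schedule arithmetic, a reading of the rule case by case, and an illustration of size.

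**1. Interval from AE baseline to ring**

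Interval = (screening to enrollment) + (enrollment to Month 1) + (Month 1 to Month 2). Enrollment to Month 1 is one month (Section 5.1) and Month 1 to ring start is 30 days (Section 6.3.1).

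- BV-negative, enrolled at screening: 0 + 30 + 30 = about 60 days.
- BV-positive: 7 to 10 + 30 + 30 = about 67 to 70 days.

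This agrees with Aim 3 in Section 9.1, which refers to two months before ring use. Sections 5.1 and 5.4 also place the Month 2 visit after one month. If that meant one month from enrollment, the interval would be 0 + 30 = 30 days, or 7 to 10 + 30 = 37 to 40 days. Screening would still precede treatment and hormone stopping, so the point does not depend on which is meant.

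**2. Who changes state in that interval**

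- Women BV-positive at screening, whose treatment starts after the AE baseline.
- Main-study women on hormonal contraception at screening. The sub-study criteria in Section 4.1.1 exclude use within the past 2 months.

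The documents do not split the planned 120 women by BV status, hormone use or symptoms at screening. The number affected could be anywhere from 0 to 120.

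**3. The rule applied case by case**

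- Absent at screening, appears on the ring: AE.
- Present at screening, on the ring at a higher grade than at screening: AE, under the severity sentence.
- Present at screening, resolved by Month 2, returns on the ring at the same or a lower grade: not an AE if the increase is measured from screening; an AE if it is measured from the pre-ring state. The text does not say which.
- Present at screening, eased by Month 2, worsens on the ring but not beyond the screening grade: the same ambiguity.

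The gap is the last two cases.

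**4. Reference points used elsewhere in the plan**

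- Section 5.1 brings treated women back one month after enrollment to establish baseline status.
- The Aim 1 primary outcome in Section 9.1 is compared with the month before ring use.
- The AE rule alone is tied to screening.

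**5. Illustration of size (all inputs assumed)**

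Let r be the true on-ring rate of a complaint, p the share of women who had it at screening, and q the share of their on-ring events that the literal rule leaves out. Assume equal on-ring risk in women with and without the screening complaint. Then recorded rate = r x (1 - p x q). Take r = 20% and p = 30% to 60%; neither comes from the documents.

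- q = 0 (every recurrence is recorded): 20%.
- q = 1, p = 30%: 0.20 x 0.70 = 14%.
- q = 1, p = 60%: 0.20 x 0.40 = 8%.

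For these inputs the recorded rate lies between 8% and 20%. The 8% to 14% range requires that no recurrence exceeds its screening grade and that every clinician takes the literal reading, so it shows the largest loss at equal risk.

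**The case against.** The strongest reply is that the text is silent on this case and does not direct non-recording. A woman with no symptoms at Month 2 who then has discharge has gone from none to some during the study, which can fairly be called an increase. The rule also speaks of a medical condition: BV that was treated and cured, and a later ring-related discharge, need not be the same condition. Section 8.4.1 defines AEs broadly and sends doubtful cases to the principal investigator, and Section 8.5 asks for all AEs whatever the relationship. This stands to the extent that non-recording is the literal reading and not the only one. It does not remove the problem, because a coder who applies the baseline sentence as written has no evident reason for doubt, and two coders could record the same event differently.

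A second reply is that the information survives elsewhere. Discharge, pruritus and menstrual history are asked at each follow-up visit (Section 6.3), and Section 8 requires assessment for ring side effects at each visit. That is true and limits the loss to AE counts. But Section 6.3 does not mention grade, relationship or resolution, which the AE form collects, and the plan does not derive the AE outcome from the interview.

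A third reply is that the exposed group is narrower than the whole cohort. This stands. Untreated BV at the baseline applies only to women positive at screening, and the hormone point does not apply to the sub-study. The bleeding case is weaker than the discharge case: no section says that hormonal users bleed irregularly at screening, and Section 8 links irregular bleeding to continuous ring use.

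**Conclusion.** The point holds as a poorly chosen and incompletely specified reference time. Screening precedes the ring by about two months and, for some women, precedes BV treatment or hormone stopping. On the literal reading, a complaint that clears or eases before Month 2 and returns at no higher than its screening grade is left out of the AE count. The reported on-ring genital AE rate may therefore be too low, mainly among women symptomatic at entry. A secondary objective and one Aim 1 secondary outcome are affected; no primary outcome depends on the rule.

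A reader might infer that ring-related complaints matching a screening complaint are never recorded. The documents do not support that: the severity sentence captures worsened complaints, and a clinician may judge a discharge to be a new condition or refer it. Nor do they establish that the rate is in fact biased low, or by how much. The 8% to 14% range rests on an assumed 20% true rate, an assumed 30% to 60% share with the screening complaint, equal risk, and the strictest reading of the rule.

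**What to change.** Amend Section 8.5 as follows.

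- For ring-emergent AEs, take the Month 2 assessment immediately before insertion as the reference. Record as an AE any sign or symptom that is absent or of lower grade at Month 2 and that starts, recurs or worsens after insertion, whether or not it was present at screening.
- Keep the screening baseline for events before insertion, and flag each AE on the CRF as starting before or after ring start.
- In Section 9.1, state that the Aim 1 genital AE outcome uses this definition.

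The cost is small: protocol wording and one CRF field. Symptoms are already collected by interview and questionnaire at Month 2 and at later visits (Sections 6.3.3 to 6.3.6), although the Month 2 record must carry a grade for the comparison to work. There are two consequences to accept. The reported AE rate will be higher, and it will include some symptoms of BV recurrence; the monthly Amsel and Nugent assessments allow events with and without concurrent BV to be shown separately. Also, AE counts before and after insertion will use different references, so the on-ring rate should be reported in its own right and a before-after ratio of AE counts read with care.
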